### Sample size Estimation and Power

**Analysis:** Table 2 shows sample size estimations based on two-sample t conducted across difference scores between groups. We expect to enroll 22 subjects but in accounting for ~10% attrition, a total of 24 subjects will be enrolled.

Table 2: Sample Size Estimation

Aim	Metric	cPMD vs. iM1		Alpha	80% 85% 90% 95%			
		UEFM	IHI		14	16	18	22
Aim 1		9±1.41 vs. 4.3±3.56	-9.25±5.89 vs. 6±14.05	0.05	14	16	18	22
Aim 2				0.05	20	22	26	30
Aim 3	Ipsilateral MEP	311.63±29.96 vs. 255.75±93.29		0.05	22	24	38	46
Aim 4	DTI $\alpha$ UEFM	15% diff. in slopes		0.05	18	20	23	28

**IMPACT:** While greater damage produces greater impairment following stroke, it also generates a widespread plastic response involving the intact cortices in the contralesional hemisphere. Although this response may not be sufficient to support complete recovery, it is likely to support more recovery than what is otherwise possible to achieve [4]. Demonstrating that facilitating these intact areas can lead to restoration of paretic-limb function in patients who fail to benefit from any therapies on account of extensive damage will carry tremendous clinical impact, provide the impetus to develop targeted therapies and depart from conventional beliefs that have always disparaged the potential offered by the intact hemisphere.

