**AIM 1: Determine the effect of facilitating cPMd on upper-limb impairment, functional abilities, proximal control and patient-reported disability.** *Hyp 1: Facilitation of cPMd will lead to greater reduction in impairment and disability and to superior improvements in functional ability and proximal reaching control than facilitation of iM1.*

**AIM 2: Investigate the effects of facilitating cPMd on inter-hemispheric connectivity.** *Hyp 2: Facilitation of cPMd will lead to greater reduction of IHI imposed upon iM1 and a larger increase in cPMd-to-iM1 functional connectivity compared with facilitation of iM1.*

**AIM 3: Investigate the effects of facilitating cPMd on uncrossed output.** *Hyp 3: Facilitation of cPMd will lead to greater excitation of uncrossed output to the paretic upper limb compared with facilitation of iM1.*

**AIM 4: Explore how ipsilesional corticospinal damage influences the response to facilitation of cPMd.** *Hyp 4: Improvements elicited with facilitation of cPMd vs. iM1 will vary as a function of the degree of damage to ipsilesional corticospinal pathways.*

**IMPACT:** In line with the mission of the AHA to build healthier lives for all, the proposed project will offer the most disadvantaged patients, those who typically cannot improve with conventional therapies, a unique opportunity to benefit from a novel brain stimulation approach tailored to their mechanism of plasticity. As such, the project will spearhead the development of targeted therapies to supplant generic approaches. In a broader sense, the project will revolutionize the understanding of stroke recovery in the fields of rehabilitation and neurology that generally have disparaged the potential of uninjured contralateral motor areas- neural resources consistently viable to support paretic-limb function in the most-affected patients.

**Figure 1: Scientific Premise:** Stimulation delivered to facilitate the excitability of the uninjured (contralateral) motor cortices will lead to improvement in proximal (e.g., reaching) and distal (e.g., grasp/grip) paretic-limb function in patients with extensive damage to ipsilesional pathways (Aim 1). Mechanisms will involve strengthening of inter-hemispheric connectivity (Aim 2) and excitation of uncrossed pathways (Aim 3). Improvements will vary as a function of the degree of ipsilesional damage (Aim 4).

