## PRELIMINARY APPROACH

[figure not shown]
Published and preliminary data acquired in our ongoing and recent AHA studies (Grant-in-Aid and Beginning Grant-in-Aid) and an NIH K01 study has provided support for our scientific premise. Data was acquired as part of short-term and long-term experiments.

**SHORT-TERM EXPERIMENT:** Moderately/severely-impaired patients with extensive damage who fail to improve with the conventional approach show robust improvements in paretic-limb movement with novel approach involving facilitation of cPMd [3]: Fifteen

patients with mild to severe impairment after chronic stroke ( $\geq 6$  months) received single sessions of facilitation of cPMd, facilitation of iM1 (conventional approach), and facilitation of a control region, contralesional M1 (cM1), in a randomized, sham-controlled, crossover study. Facilitation was delivered using rTMS. Sessions were separated by  $\geq 1$  week to allow for washout of effects. At baseline, impairment (Upper Extremity Fugl-Meyer, UEFM) and corticospinal damage (indexed using DTI as Fractional Anisotropy, FA) were measured. Outcomes included paretic-limb reaching speed and IHI exerted from the contralesional upon the ipsilesional motor cortices (studied using TMS) [3].

In line with findings of other studies, we observed that moderately/severely-impaired patients with extensive ipsilesional damage failed to achieve any improvement in paretic-limb reaching with facilitation of iM1 [15, 25, 28, 36-38]. But a unique finding was that these same patients achieved significant improvement with facilitation of cPMd ( $t_{13} = 2.57$ ;  $p = 0.012$ ; Fig. 2A). Effect of facilitating cPMd was related to a reduction in IHI; patients who became faster at paretic-limb reaching with cPMd facilitation experienced greater reduction in IHI from contralesional upon ipsilesional cortices, i.e., better inter-hemispheric connectivity ( $r=0.75$ ,  $p < 0.001$ , Fig. 2B).

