**STATISTICAL ANALYSIS:** For analysis of aims 1, 2 and 3, linear mixed effects models will be used to compare change in UEFM (primary endpoint), WMFT rate, functional ability, grip strength, SIS, IHI, functional connectivity, and ipsilateral MEP area from baseline to end-of-treatment (and 3-month follow-up) between groups. Models will account for spasticity, baseline wrist extension (none;  $\leq 10^\circ$ ;  $> 10^\circ$ ), lesion size/location, time post-stroke, side of paresis, biologic variables (e.g., sex) and handedness. Bivariate (Pearson's) correlation will be used to explore relationships between change in function and change in IHI, functional connectivity and ipsilateral MEP area. Chi-square or Fisher's Exact test will help compare the frequency of responders (those achieving  $\geq 5.2$ -point UEFM gain [84]) and patients showing restoration of ipsilesional MEPs (MEP+) between groups. For aim 4, regression models will capture the influence of baseline  $FA_{\text{Asymmetry}}$  upon improvements associated with facilitation of cPMd vs. iM1, and separately the influence of baseline UEFM and wrist extension.

Additional data analysis will be conducted using quantum machine learning (QML) to develop a classification model for assessing the functional capacity of stroke patients to use the affected upper extremity. We will utilize behavioral outcome measures signifying the functional capacity collected during this study. The ultimate goal of this analysis is to discern variations in functional capacity among individuals affected by stroke for tailoring rehabilitation interventions to each patient's specific needs.

**Potential Pitfalls and Alternative Solutions:** *If not all patients can elicit ipsilateral MEPs in the paretic muscle*, we will compare groups upon the frequency of evidence of these MEPs after treatment (Chi-square/Fisher's Exact) [4, 52, 57, 58, 60-73]. *If effects of cPMD facilitation are weak*, we will perform sub-group analyses based on baseline wrist extension to determine which category of patients shows the best response. We will also determine what level of baseline FAAsymmetry, connectivity, impairment (UEFM) predicts response vs. non-response (based on attainment of 5.2-point UEFM gain [84]). *Anticipating that cPMD facilitation may have effects on bilateral control*, we will adopt bimanual test used in our recent study [159].

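### Table 2's Aim 4 row claims 80–95% power with 18–28 patients for a 15% difference in slopes; a relative difference of that size has about 5–12% power for assumed within-arm correlations of 0.5–0.9.

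*Protocol*

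**What the plan says.** Protocol, Specific Aims, Hypothesis 4: "Improvements elicited with facilitation of cPMd vs. iM1 will vary as a function of the degree of damage to ipsilesional corticospinal pathways". Under Statistical Analysis, "regression models will capture the influence of baseline" FA asymmetry on the gains seen with cPMd against iM1 facilitation. Together these describe a test of whether the regression of improvement on FA asymmetry differs between arms, that is, an arm-by-FA interaction.

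Protocol, Sample size Estimation and Power Analysis, Table 2: the Aim 4 row is labelled "DTI $\alpha$ UEFM", its effect is "15% diff. in slopes", alpha is 0.05, and the sample sizes are 18, 20, 23 and 28 for 80, 85, 90 and 95% power. The sentence introducing the table says that it rests on a "two-sample t conducted across difference scores between groups". On trial size it says: "We expect to enroll 22 subjects but in accounting for ~10% attrition, a total of 24 subjects will be enrolled".

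No slope, residual SD, spread of FA asymmetry or R-squared is given for Aim 4. The 15% is not defined as relative, absolute or variance explained. The SAP does not mention an Aim 4 analysis.

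**The concern.** A difference between two regression slopes is hard to estimate with about ten patients per arm, and 15% of a slope is a small difference. High power for it at a total of 18 to 28 patients is therefore surprising on its face. The test named for the table compares mean change scores and cannot give a sample size for a slope comparison, so the row must come from some other calculation that is not described.

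The Protocol presents Aim 4 as the route to a damage threshold for selecting responders. Someone who took the 80–95% at face value could give a null interaction more weight than a trial of this size can support.

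**Working it through.** **Inputs from the Protocol.** Alpha 0.05; effect 15%; N = 18/20/23/28; 22 evaluable patients planned.

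**Assumptions.** Two-sided test, total N, equal arms, and the same FA spread and residual SD in both arms. Two-sided testing at total N is a fair guess because the Aim 1 and Aim 2 rows come out close that way: 14/16/18/20 against the stated 14/16/18/22, and 18/22/24/30 against the stated 20/22/26/30. The within-arm correlation r between FA asymmetry and UEFM gain is not given, so it is varied.

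**Test.** Let δ be the slope gap in residual SD per FA SD. The interaction t-test has N − 4 df and noncentrality δ√N/2. Equivalently, f² = δ²/4.

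**Step 1: what the stated cells imply.** Solving for δ:

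| N | power | δ | f² |
|---|---|---|---|
| 18 | 80% | 1.42 | 0.50 |
| 20 | 85% | 1.43 | 0.51 |
| 23 | 90% | 1.43 | 0.51 |
| 28 | 95% | 1.42 | 0.50 |

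The row is internally consistent: all four cells correspond to one effect, f² of about 0.5 (partial R² about 0.34).

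**Step 2: what a 15% relative difference gives.** With reference-arm correlation r, the slope in residual SD per FA SD is b = r/√(1 − r²), and δ = 0.15b. At r = 0.75, b = 0.75/√0.4375 = 1.134, δ = 0.170 and f² = 0.007.

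| r | δ | power, N=18 | N=22 | N=28 |
|---|---|---|---|---|
| 0.5 | 0.087 | 5.3% | 5.4% | 5.6% |
| 0.75 | 0.170 | 6.3% | 6.7% | 7.2% |
| 0.9 | 0.310 | 9.4% | 10.6% | 12.3% |
| 0.95 | 0.456 | 14.7% | 17.4% | 21.3% |

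Simulation agrees at r = 0.75: 6.1% at N=18 and 6.8% at N=28. When FA varies at random the values run slightly lower, for example 12.7% at r = 0.95 and N=18.

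To have δ = 1.42 with a 15% difference, b must be 1.42/0.15 = 9.5, so r is about 0.994. At r = 0.75, 80% power would need about 1,088 patients; at r = 0.9, about 330.

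Other conventions do not close the gap. One-sided testing at r = 0.75 gives 9.7–11.4%. Reading the cells as per-arm sizes gives 7.9–9.6%.

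**Step 3: size of the mismatch.** At r = 0.75, the gap that the cells need is 1.42/1.134 = 125% of the reference slope, so the second slope would have to reverse sign or more than double. Against a 15% difference that is a factor of 1.42/0.170, about 8.

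**Step 4: a reading that reproduces the row.** Suppose 15% means 15 points of R² added by the interaction to a base R² of 0.5625. Then f² = 0.15/(1 − 0.5625 − 0.15) = 0.15/0.2875 = 0.52. Power at 18/20/23/28 is 81.3/85.8/90.7/95.6%, and the smallest N reaching 80/85/90/95% are exactly 18, 20, 23 and 28. The fit depends on the base: power at N=18 falls to 62.5% for a base of 0.40 and to about 51% for 0.25. A partial R² of 0.15 gives 38–57% across the four sizes.

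**Step 5: what the planned trial can detect.** At N=22 and 80% power, δ is about 1.26 (noncentrality 1.26 × √22/2 = 2.95, 18 df).

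**The case against.** The strongest defence is Step 4. The Protocol reports one correlation of 0.75, its square is 0.5625, and entering that as the base R² returns all four cells exactly. On that view nothing was miscalculated and only the label is loose. What stands is that the cells are coherent and that an arithmetic slip has not been shown. What does not stand is that this clears the row. An R² increment is not a difference in slopes, and no base R² is stated for Aim 4. The 0.75 belongs to another relationship, reaching-speed gain against change in interhemispheric inhibition in the short-term study ("Effect of facilitating cPMd was related to a reduction in IHI"), not FA asymmetry against UEFM gain.

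A reader might go further and infer that power is 6–7%. The documents do not yield that figure: it needs both the relative reading of 15% and a correlation near 0.7–0.75 that they do not state for these variables. A reader might also infer that the trial would treat a null interaction as proof that damage does not modify the effect, or that Aim 4 set the sample size. Neither is supported. The Protocol says nothing of the first. On the second, the planned 22 appears in the Aim 1, 2 and 3 rows but not in the Aim 4 row.

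It is also fair that Aim 4 is exploratory, in a pilot, and that the Protocol plans a separate search for the level of FA asymmetry that predicts response. That limits the harm.

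**Conclusion.** The concern holds in this form: the effect named in the Aim 4 row and the sample sizes beside it do not belong together. A relative 15% slope difference has about 5–12% power at 18–28 patients for r between 0.5 and 0.9, and 15–21% at 0.95, against the 80–95% claimed. This rests on a two-sided 0.05 test, equal arms and equal FA spread. The correlation is assumed, but only a value near 0.994 would rescue the claim.

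If some other effect was computed, such as an R² increment of 0.15 on a base near 0.56, then the effect is mislabelled, its key input is missing and the test is misnamed. The documents do not show which of these happened. On either reading the row cannot be relied on as written, and it is worth correcting because the correction is cheap.

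**What to change.** Remove the 80–95% power claim for a 15% slope difference. State that Aim 4 is exploratory, that the regression includes an arm-by-FA-asymmetry interaction, and that this will be reported with a 95% CI. If a detectable size is wanted, say that with 22 patients in equal arms and a two-sided 0.05 test, the gap detectable with 80% power is about 1.26 residual SD of the outcome per SD of FA asymmetry. The unit should be the residual SD; converting it to outcome SD would need another assumed correlation.

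If the row is kept, relabel the effect as what was actually computed (for example an R² increment of 0.15 with its base R² and the source of that base), give the residual SD and FA spread if slopes were used, and name the regression test in place of the two-sample t.

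This is a text change to one table row and one sentence. Sample size and data collection are unaffected. The downside is a weaker stated claim for an exploratory aim.

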Title: *A Novel Approach for Brain Stimulation in Severe Stroke*

NCT03868410

10/23/24

Statistical Analysis Summary for Results

Statistical Analysis Plan Results

Statistical analysis was performed in R 4.3.1. Shapiro-Wilks tests were used to evaluate normality of data. For each motor outcome measure, we used repeated-measures ANOVA or Friedman's test to evaluate whether the outcome changed across time, separately for each group. When the omnibus test was statistically significant, post hoc pairwise comparisons were carried out using paired t-tests or Wilcoxon signed-rank tests, and multiple comparisons were corrected using the Holm-Bonferroni method. To understand whether treatment effects differed between groups, we used independent t-tests or Wilcoxon rank sum tests to compare change scores between groups. Because we did not find any change between post-test and follow-up timepoints in either group, we focused between-group comparisons on change from pre-test to post-test and change from pre-test to follow-up. The Holm-Bonferroni method was used to correct for multiple comparisons.

For TMS outcomes, we used paired t-tests or Wilcoxon signed rank tests to evaluate whether each outcome changed across time, separately for each group. To understand whether treatment effects differed between groups, we compared change scores between groups with Wilcoxon rank sum tests. We also explored whether change in motor function (motor outcomes) were associated with change in TMS.

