## APPROACH

**Study Design and Criteria:** In a pilot, randomized-controlled, single-blind study, a target of 24 patients will be assigned to either receive facilitation of cPMd or facilitation of iM1 (conventional approach), delivered daily in conjunction with rehabilitation for 2 days/wk for 6 wks. They will be assigned to treatment groups using a stratified randomization scheme to minimize group imbalances on 4 key patient characteristics: (1) time post-stroke (<2 yrs vs.  $\geq$ 2 yrs), (2) cortical vs. subcortical stroke, (3) presence of active wrist extension vs. no wrist extension, and (4) paretic side (dominant vs. non-dominant). Assessments will be completed at baseline and at the end of treatment after 6 wks, except assessments for Aim 1 that will also be completed at screening and at 3-month follow-up visit (Table 1). Ten age matched healthy controls, fifteen age matched mild, and up to 5 moderately impaired participants (who will undergo rTMS and CCFES based-therapy) will also be enrolled to record comparative neural indices. The goal will be to establish age-based norms for healthy, mild, moderate, and severe neurophysiologic metrics related to EDC, FDI, Biceps, and Triceps muscles.

Table 1: Schedule of Assessments		Screening & Eligibility	Baseline (0 weeks)	End-of-Treatment (6 weeks)	Follow-up (3 months)
History, Physical & Neurological Examination		X			
Eligibility testing: Inability to elicit MEPs (TMS), i.e., MEP-		X			
Aim 1	Impairment (UEFM)			X	X
	Functional Ability (WMFT)		X	X	X
	Distal movement (Grasp/Grip Strength)		X	X	X
	Patient-perceived Disability (SIS-16)		X	X	X
Aim 2	IHI imposed on iM1 (TMS)		X	X	
	Inter-hemispheric connectivity (resting state fMRI)		X	X	
Aim 3	Uncrossed pathways or Ipsilateral MEPs (TMS)		X	X	
	Ipsilesional corticospinal damage (DTI)		X		
Aim 4					

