**AIM 1: Determine the effect of facilitating cPMd on upper-limb impairment, functional abilities, proximal control and patient-reported disability.** At baseline, end-of-treatment and 3-month follow-up, we will collect the following indices. *Impairment* will be measured using UEFM, one of the most widely used assessments in stroke [110]. UEFM will serve as our *primary outcome* because it is sensitive to discerning the effects of rTMS/rehabilitation [14, 45, 111-114], and has excellent reliability (ICC= 0.97), consistency (Cronbach's  $\alpha$ = 0.84) and validity [115-120]. *Functional ability* to use the paretic upper limb in a variety of tasks will be assessed using WMFT (developed by co-I, [name]). Time to complete each task will be noted and converted to rate (60/Performance Time (sec)), optimized for measurement in moderately/severely-impaired patients [83]. WMFT rate shows high validity and reliability in this population [83]. Grip strength will also be recorded with WMFT. *Proximal motor control* will be assessed using an upper extremity task. The task will characterize motor control in moderately/severely-impaired patients who typically lack adequate distal movements. *Patient's perceived disability* related to physical function will be indexed using the Stroke Impact Scale (SIS-16), a reliable (ICC= 0.94) and valid index [127, 128].

**Expected outcomes and interpretations:** Based on the findings of our AHA study, we expect that facilitation of cPMd will lead to greater improvement on UEFM, WMFT rate, grip strength, and SIS-16 than facilitation of iM1 (Fig. 3A). This finding would mean that facilitation of the intact hemisphere promotes paretic upper-limb recovery in patients who cannot rely on injured cortices due to extensive ipsilesional damage.

**AIM 2: Investigate the effects of facilitating cPMd upon inter-hemispheric connectivity.** Inter-hemispheric connectivity will be characterized using IHI collected with TMS and functional connectivity collected with resting-state fMRI (rsfMRI). IHI will serve as the *primary outcome*

because it is sensitive to capturing the effects of rTMS [3, 45, 47, 125, 129-131]. Functional connectivity will complement IHI measurement as a secondary outcome because while IHI records neurophysiologic interactions between a contralateral and a weak ipsilateral region, functional connectivity defines "global" interactions across multiple regions.

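### The SAP reports unadjusted change-score tests where the protocol names covariate-adjusted mixed models for UEFM, and neither labels nor explains the change

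*SAP*

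**What the plan says.** Protocol, STATISTICAL ANALYSIS: "linear mixed effects models will be used to compare change in UEFM (primary endpoint" and other outcomes, "from baseline to end-of-treatment (and 3-month follow-up) between groups". The models are to account for spasticity, baseline wrist extension in three categories, "lesion size/location, time post-stroke, side of paresis, biologic variables (e.g., sex) and handedness". Baseline UEFM is not on that list, although the Aim 1 section states: "At baseline, end-of-treatment and 3-month follow-up, we will collect the following indices".

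Protocol, Study Design and Criteria: allocation uses a "stratified randomization scheme to minimize group imbalances on 4 key patient characteristics", namely time post-stroke, cortical or subcortical stroke, active wrist extension, and paretic side.

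Protocol, Sample size Estimation and Power: Table 2 rests on a "two-sample t conducted across difference scores between groups".

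SAP: the document is headed "Statistical Analysis Summary for Results", is written in the past tense, and explains its focus on two contrasts by an observed result. For each motor outcome it reports within-group tests over time and then, between groups, "we used independent t-tests or Wilcoxon rank sum tests to compare change scores between groups", with Holm-Bonferroni correction. It mentions normality testing but gives no rule linking that to the choice of test. It does not mention a mixed model, a covariate, a stratification factor or a departure from the protocol. It does not name UEFM. That UEFM falls under the motor outcomes is an inference, but a safe one.

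**The concern.** Hypothesis 1 rests on the between-group contrast in UEFM. The protocol gives that contrast one method and the SAP reports another. Because the SAP was written with results known, a reader cannot treat it as a replacement fixed in advance, and nothing in it says that a replacement took place. With about 22 patients, reasonable analyses can fall on opposite sides of 0.05. The reader therefore needs three things: that the method changed, why, and whether the result holds when the comparison is adjusted for baseline. The SAP supplies none of them, and it leaves open whether the UEFM p-value came from a t-test or a rank-sum test.

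**Working it through.** **1. Reproducing the protocol's sizing.** Table 2 gives UEFM changes of 9±1.41 and 4.3±3.56, a difference of 4.7, at alpha 0.05. I assume 1:1 allocation, which the protocol does not state. A two-sided unequal-variance t-test gives total N of 14, 16, 18 and 22 for 80, 85, 90 and 95% power, exactly as printed. At 11 per arm, SE = √((1.41² + 3.56²)/11) = 1.15 and power is 96.4%. The trial was therefore sized on the unadjusted test that the SAP lists.

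**2. Stratification factors against the protocol's covariates.**

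| Factor at randomisation | Covariate in the protocol's model |
|---|---|
| Time post-stroke | Time post-stroke |
| Active wrist extension | Baseline wrist extension |
| Paretic side, dominant or not | Side of paresis with handedness |
| Cortical or subcortical | No clear counterpart |

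The Aim 4 section defines lesion location as posterior limb of the internal capsule or not, which is a different split from cortical or subcortical. Three of the four factors have counterparts.

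**3. What baseline adjustment adds.** The protocol's LONG-TERM EXPERIMENT paragraph gives iM1 SDs of 11.07 before and 10.34 after treatment; Table 2 gives a change SD of 3.56. I assume these SDs for both arms.

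- Correlation = (11.07² + 10.34² − 3.56²)/(2 × 11.07 × 10.34) = 0.947.
- Slope of post on pre = 0.947 × 10.34/11.07 = 0.885.
- Residual SD = 10.34 × √(1 − 0.947²) = 3.32.
- Unadjusted, 11 per arm: SE = 3.56 × √(2/11) = 1.52; power for 4.7 points 83.8%; half-width 2.086 × 1.52 = 3.17.
- Baseline-adjusted: SE = 3.32 × √(2/11) × √(19/18) = 1.46, where the last factor allows for chance baseline imbalance; power 86-87%; half-width 2.093 × 1.46 = 3.05.

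Simulated median half-widths are about 3.1 and 3.0. The gain is small because the change score already removes about 88% of any baseline imbalance. A one-SE imbalance, 11.07 × √(2/11) = 4.7 points, leaves about (1 − 0.885) × 4.7 = 0.5 points.

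**4. Adding the four stratification factors.** This is a reduced model, not the protocol's own. It was simulated with 24 randomised, 22 evaluable, and allocation by stratified blocks or minimisation.

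- Power is about 80-81% if the factors are unrelated to outcome, against 83-84% for the t-test.
- Power is about 86-89% if they explain 20% of residual variance.
- The model and the t-test disagree on p<0.05, before any Holm correction, in about 10-14% of trials at 4.7 points. Disagreement runs both ways: in one case with unrelated factors, 6.5% lost significance and 5.2% gained it.
- With Table 2's own SDs the disagreement falls to about 3-6%.

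**5. Type I error.** Under the null with normal data and 11 per arm, the t-test rejects in 4.9% of trials, the rank-sum test in 4.7%, and at least one of the two in 5.8%. If the factors are prognostic, the t-test under stratified allocation is slightly conservative, at about 4%.

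**The case against.** The strongest defence is that the SAP's test is the simpler one and the one used for sizing. The full protocol list also costs about 9 df: wrist extension 2, and one each for spasticity, lesion size, lesion location, time, side, sex and handedness. That leaves 22 − 2 − 9 = 11 residual df. Allowing for chance imbalance, the list must explain about 9/19 = 47% of the variance to break even. This stands as a good reason to simplify, but the SAP does not give it, and sizing on a t-test does not replace the analysis that the protocol names.

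It is also fair that the SAP is a methods summary without numerical results, so it cannot be faulted for not printing an adjusted estimate. The point is that it describes no adjusted analysis. Normality testing implies how the test was chosen, and leaving the choice open costs at most about one percentage point of alpha in the setting of step 5. The naming gap matters for clarity more than for error control.

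The disagreement rates in step 4 concern a model found in neither document and do not apply the SAP's Holm correction. They show how sensitive a 22-patient comparison is. They do not measure the effect of departing from the protocol's model.

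A reader might infer more than the documents support:

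- *That the reported comparison is biased or its type I error inflated.* Step 5 shows neither for the unadjusted tests.
- *That the contrasts were chosen to suit the data.* The two contrasts kept, baseline to end-of-treatment and to follow-up, are those in the protocol.
- *That omitting baseline UEFM is itself a departure.* The protocol's covariate list does not contain it.

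**Conclusion.** The point holds as an unlabelled and unexplained change in the primary analysis, in a document written after results, with the UEFM test left unnamed and no adjusted analysis described. Its statistical cost is modest: about 2 to 3 percentage points of power and about 0.1 point of half-width forgone by not adjusting for baseline. These figures assume a change SD of 3.56 in both arms, the pre and post SDs in step 3, 22 evaluable patients and 1:1 allocation. With Table 2's own SDs the unadjusted test already has about 96-97% power, so power is not the argument. The documents give no figure for how strongly any stratification factor predicts UEFM change, so the value of adjusting for them cannot be settled from the plan. What is at stake is whether the reader can see that the method changed and whether the Hypothesis 1 result is robust.

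**What to change.** 1. State in the SAP that the t and rank-sum tests differ from the mixed models in the protocol's statistical analysis section, give the actual reason, and name the test used for UEFM.
2. Beside the reported tests, give a UEFM comparison adjusted for baseline UEFM at end-of-treatment and at 3 months, by ANCOVA at each visit or a mixed model. Label it post hoc and supportive, report it whatever it shows, and leave the reported tests in place.
3. Optionally, add the four stratification factors as main effects, coded as at randomisation.

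The cost is a few sentences and one or two model runs on data already collected. Baseline adjustment uses 1 df, leaving 19. The four factors use 4 more, leaving 15. If those factors are unrelated to outcome, that model has about 2 to 3 points less power than the t-test, which is why it is optional. No trial procedure changes.
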